10. Have received vaccinations within 4 weeks before Screening or have any vaccinations planned during the study.
11. Have a history of malignancy, including malignant thymoma, or myeloproliferative or lymphoproliferative disorders at any time, unless deemed cured by adequate treatment with no evidence of recurrence for ≥ 5 years before Screening. Patients with completely excised non-melanoma skin cancers (such as basal cell carcinoma or squamous cell carcinoma) or cervical carcinoma in situ would be permitted at any time.
12. Have a history of cerebrovascular accident or myocardial infarction within the last 12 months before Screening, or current severe/unstable angina, arrhythmia, symptomatic congestive heart failure New York Heart Association (NYHA) class III or IV, or uncontrolled hypertension.
13. Have clinical evidence of significant unstable or uncontrolled acute or chronic diseases (i.e., cardiovascular, pulmonary, hematologic, gastrointestinal, endocrinologic, hepatic, renal, neurologic, malignancy, or infectious diseases) which, in the opinion of the Investigator, could confound the results of the study or put the patient at undue risk.
14. Major past surgery (e.g., heart valve replacement, hip replacement) that, in the opinion of the Investigator, poses a risk to patient's safety or interferes with the study evaluation, procedures or completion.
15. Thymectomy when performed < 3 months prior to Screening.
16. History or presence of alcoholism or drug/chemical/substance abuse within 2 years before Screening per Investigator's opinion.

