5.3.4 Early Discontinuation from the Study Treatment or Study

The criteria for enrollment and randomization are to be followed explicitly. If it is noted that a patient who does not meet the inclusion and exclusion criteria is inadvertently randomized and dosed, the [Medical Monitor](#) at Sponsor's designated CRO (Quintiles) and the Sponsor's [Medical Director](#) must be contacted immediately for discussion on how to proceed with the patient. The patient should be discontinued from the study if there is any compelling safety concern for the patient to continue. The various scenarios that may occur leading to discontinuation of the patient from study and/or treatment is detailed in [Table 2](#).

Table 2 Potential Scenarios for Early Discontinuation from Study and Treatment

Scenario	Discontinuation from Study Treatment	Discontinuation from Study	Replacement if necessary
Safety Concern during Treatment period: In case of a safety concern during Treatment period , Medical Monitor should be consulted and the safety and efficacy assessments per Follow-up period of Table 1 (Visit 9 to Visit 16) must be completed wherever possible.	Discontinue patient from Study Treatment.	Patient does not need to be discontinued from the study depending on the severity and nature of safety event but discontinuation from the study needs to be discussed with the Medical Monitor and/or Sponsor's Medical Director . Wherever possible and appropriate/safe, the patient should continue the schedule of assessments for the Follow-up Period of Table 1 (Visit 9 to Visit 16).	Patients will be analyzed as part of Safety and Efficacy analysis and such a patient will not be replaced.
Safety Concern after Treatment period: In case of a safety concern after Treatment period , the safety and efficacy assessments per Follow-up period of Table 1 (Visit 9 to Visit 16) must be completed where possible and Medical Monitor should be consulted.	Not Applicable.	Patient does not need to be discontinued from the study depending on the severity and nature of safety event but discontinuation from the study needs to be discussed with the Medical Monitor and/or Sponsor's Medical Director . Wherever possible and appropriate/safe, the patient should continue the schedule of assessments in the Follow-up Period of Table 1 (Visit 9 to Visit 16).	Patients will be analyzed as part of Safety and Efficacy analysis and such a patient will not be replaced.

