Disease deterioration during Treatment period	After consultation with the Medical Monitor , discontinue patient from Study Treatment, initiate rescue therapy and follow-up for 30 days after the early discontinuation visit or until satisfactory resolution/stabilization.	After consultation with Medical Monitor and prior to start on rescue therapy, all Visit 16 assessments should be completed. Patients will be discontinued from the study and followed up for safety for an additional 30 days or until satisfactory resolution/stabilization.	Patients will be analyzed as part of Safety and Efficacy analysis and such a patient will not be replaced
Disease deterioration after Treatment period: In case of disease deterioration after Treatment period , the safety and efficacy assessments per Follow-up period of Table 1 (Visit 16) must be completed along with a follow-up for 30 days after the early discontinuation visit or until satisfactory resolution/stabilization where possible and Medical Monitor should be consulted.	Not Applicable.	Patient's study continuation must be assessed by the Investigator, discussed with the Medical Monitor and/or Sponsor's Medical Director based on clinical examination. Possible examples of worsening include: 
 • Severe deterioration where it may not be possible for patient to continue in the study. • The "End of Treatment Effect" whereby the patient's condition is worsening after any initial improvement while on the study. Prior to initiating rescue therapy, all Visit 16 assessments should be completed and patient should be followed up for safety for an additional 30 days or until satisfactory resolution/ stabilization.	Patients will be analyzed as part of Safety and Efficacy analysis and such a patient will not be replaced

Scenario	Discontinuation from Study Treatment	Discontinuation from Study	Replacement if necessary

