Voluntary Discontinuation from IMP or Major Protocol Deviation(s) possibly leading to (Details in a separate Manual) discontinuation from IMP during Treatment period: The Schedule of Assessments for dosing and safety and efficacy evaluations per Table 1 must be performed whenever possible and must be discussed with the Medical Monitor on a case-by-case basis.	In case of voluntary discontinuation during Treatment period or any major protocol deviation(s) possibly leading to discontinuation from IMP during treatment period, a patient should be discontinued from the study treatment.	Patient does not need to be discontinued from the study but discontinuation from the study needs to be discussed with the Medical Monitor and/or Sponsor's Medical Director . And wherever appropriate, patient should continue the schedule of assessments.	Patient will not be replaced if he/she receives at least 3 infusions and completes the Follow-up assessments as indicated in Table 1 with at least 2 weeks of Follow-up post last dose. Patient may be replaced if he/she receives less than 3 infusions and/or cannot complete at least 2 weeks of Follow-up post last dose as indicated in Table 1 .
Major Protocol Deviation(s) (Details in a separate Manual) after Treatment period: The safety and efficacy assessments per Follow-up period of Table 1 (Visit 8 to Visit 16) must be completed where possible and Medical Monitor should be consulted.	Not Applicable.	Patient does not need to be discontinued from the study but discontinuation from the study needs to be discussed with the Medical Monitor and/or Sponsor's Medical Director . Wherever appropriate, patient should continue the schedule of assessments.	Such patients may only be replaced they cannot complete at least 2 weeks of Follow-up post last dose as indicated in Table 1 .

During the study, in case of situations that occur apart from the scenarios described above, the decision to replace patients must be made on a case-by-case basis in consultation with the [Medical Monitor](#) at the Sponsor's designated contract research organization (CRO, Quintiles) and/or the [Medical Director](#) at the Sponsor's end.

In addition, patients must be discontinued early from the study in the following circumstances:

- Pregnancy.
- Lack of efficacy as judged by the Investigator.
- Emergency unblinding.
- Physician decision.
- Lost to follow up.
- On request of the Sponsor.

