6.7 Unscheduled Visit

It is at the Investigator's discretion to initiate an unscheduled visit, if deemed necessary for the patient's safety and well-being (e.g., for a safety FU after completion or discontinuation

argenx
ARGX-113-1602, Version 2.0
ARGX-113

to monitor any unresolved AE). All such visits will be documented along with any additional required documentation based on the nature of unscheduled visit.

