7.9.1 Prohibited Medications during the Study

The following medications will not be permitted during the study and will result in early discontinuation from the study when they need to be started:

- Any IgG therapy;
- Introduction of a new immunosuppressant that the patient was not already taking at Screening;
- Dose increase in the immunosuppressant that the patient was taking from Screening;

- Rituximab, belimumab, eculizumab, or any monoclonal antibody for immunomodulation;
- Vaccines;
- Therapeutic PE.

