7.9.2 Rescue Therapy

Patients are eligible for rescue therapy as judged by the Investigator on the basis of parameters such as changes in MGQoL15r, MG-ADL, QMG, and MGC on any study day. Rescue therapy will be determined by the Investigator based on an overall clinical assessment and could include IVIg, PE, increase in the dose and frequency of SoC or any other treatment chosen by the Investigator. In this study, ARGX-113 may interfere with the efficacy or duration of efficacy of IVIg considering the half-life of IVIg. Additional details about ARGX-113 is present in [Section 2.2](#).

In case a patient needs rescue therapy according to the treating Investigator, the [Medical Director](#) at the Sponsor should be informed in addition to the [Medical Monitor](#) at the Sponsor's designated contract research organization (CRO, Quintiles); where possible prior to actual implementation of the rescue therapy.

If rescue therapy is administered, patients need to be discontinued from the study. For patients who discontinue the study early, all the procedures listed for the Early Discontinuation (ED) visit (same procedures as for the End-of-Study [EoS] visit or Visit 16) in the Schedule of Assessments ([Table 1](#)) are to be performed (early discontinuation visit) prior to starting on rescue therapy wherever possible.

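### Section 7.9.1 ends all study follow-up when a listed medication is started for a non-MG reason, even after the last infusion; continuing scheduled safety visits would be a cheap, low-priority improvement

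*Protocol*

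**What the plan says.** Protocol 7.9.1 bars IgG therapy, a new or increased immunosuppressant, immunomodulating monoclonal antibodies, vaccines and plasma exchange. It says that these "will result in early discontinuation from the study when they need to be started". There is no exception for the indication, for the period after dosing, or for Medical Monitor judgement.

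After exit the patient has one ED visit with the Visit 16 assessments (6.6), which include laboratory tests, vital signs and ECG. Beyond that there are 30 days of AE/SAE assessment (5.3.5), unscheduled visits at the Investigator's discretion, for example "for a safety FU after completion or discontinuation" (6.7), and extra samples if clinically indicated (8.1.2). SAP 6.4 maps ED data to one next visit. It lists unscheduled values but keeps them out of by-visit summaries. SAP 7.3 imputes nothing.

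Neighbouring rules go both ways:
- Exit is also mandatory for rescue (7.9.2): "If rescue therapy is administered, patients need to be discontinued from the study". The same holds in Table 2 (5.3.4) for deterioration during treatment: "Patients will be discontinued from the study and followed up for safety for an additional 30 days or until satisfactory resolution/stabilization".
- Exit is not the default in the Table 2 safety-concern rows: "Patient does not need to be discontinued from the study depending on the severity and nature of safety event". Nor is it in the major-deviation rows: "Patient does not need to be discontinued from the study but discontinuation from the study needs to be discussed".

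Table 2 has no row for prohibited medication, and the list of mandatory exits below it does not name one.

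**The concern.** Safety and tolerability is the only primary objective, and Section 4.1 names laboratory assessments, vital signs and ECG in the primary endpoint. The last infusion is on Day 22 and follow-up runs to Day 78. For 8 of the 11 weeks after first dose, therefore, the exit rule prevents no dosing and only ends scheduled observation. Leaving the study is an understandable way to keep efficacy and PD data clean, but safety data do not need it. With about 12 patients per arm, each by-visit safety row is small, and one early exit removes a visible share of it.

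The reach is narrow. MG rescue accounts for most of the listed items and is outside this point. Planned vaccination is already an exclusion (criterion 10: "Have received vaccinations within 4 weeks before Screening or have any vaccinations planned during the study"). What is left is mainly an unplanned vaccine, or IgG or an immunosuppressant given for a reason other than MG.

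**Working it through.** The plan states no figure on this point. Its sample-size figures (10 or 12 per group at 80% power, Appendix 14.6) do not depend on it.

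**Inputs** (Table 1; Sections 6.5.2, 6.5.3, 5.3.5; SAP 6.4)
- Follow-up laboratory visits 9 to 16: Days 29, 36, 43, 50, 57, 64, 71, 78 (8 visits).
- Follow-up vital-sign visits 9, 10, 11, 12, 14, 16: Days 29, 36, 43, 50, 64, 78 (6 visits).
- The ED visit fills one later visit.
- AE/SAE assessment runs for 30 days after the ED visit, taken here as the minimum.

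**Formulas for exit on day d**
- Blank visits = max(0, scheduled visits after d − 1).
- AE capture relative to plan = (d + 30) − 78. It is negative before Day 48, zero on Day 48 and positive after it.

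| Exit day | Laboratory visits blank | Vital-sign visits blank | AE capture against Day 78 |
|---|---|---|---|
| 22 | 8 − 1 = 7 | 6 − 1 = 5 | 26 days short |
| 36 | 6 − 1 = 5 | 4 − 1 = 3 | 12 days short |
| 50 | 4 − 1 = 3 | 2 − 1 = 1 | 2 days beyond |

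**Average over Days 23 to 78** (56 days, assumed equally likely)
- Laboratory visits after exit, summed over exit days: 6 + 13 + 20 + 27 + 34 + 41 + 48 + 55 = 244. The ED visit fills one for each of the 55 exit days before Day 78: 244 − 55 = 189, and 189/56 = 3.4.
- Vital signs: 6 + 13 + 20 + 27 + 41 + 55 = 162; 162 − 55 = 107, and 107/56 = 1.9.
- AE capture: shortfalls on Days 23 to 47 are 25 + 24 + … + 1 = 325; excesses on Days 49 to 78 are 1 + 2 + … + 30 = 465. Net (465 − 325)/56 = 2.5 days longer.
- Scheduled visits that continued follow-up would add: 244/56 = 4.4 on average, at most 8.

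No laboratory visit is left blank for exits on the last 8 days, and no vital-sign visit for exits on the last 15. No ECG is lost in number, because the only scheduled ECG after Visit 7 is at Visit 16 and the ED visit includes one.

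**Arm level.** Twelve patients have 12 × 8 = 96 follow-up laboratory visits. With 0, 1 or 2 affected patients (assumed), the average share blank is 0%, 3.375/96 = 3.5% or 6.75/96 = 7.0%. If all exits fall on Day 22 it is 0%, 7/96 = 7.3% or 14/96 = 14.6%.

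**Frequency.** None is documented. If 1%, 2%, 5% or 10% of patients needed such a medication (assumed), the expected number among 24 would be 0.24, 0.48, 1.2 or 2.4, and the chance of at least one, 1 − (1 − p)^24, would be 21%, 38%, 71% or 92%.

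**The case against.** The strongest reply is that little is lost. The number affected may be zero. Safety data are described and not tested (SAP 16). The ED set, AE follow-up, optional visits and complete listings are a reasonable package for a rare event, and values after IgG or a new immunosuppressant would be confounded anyway. Most of this stands and limits the point to low priority. It does not justify stopping visits that are already scheduled, because confounded safety values can be flagged.

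Four stronger readings are tempting, and the documents do not support them.
- *The protocol contradicts itself.* Mandatory exit in 7.9.1 agrees with 7.9.2 and with the Table 2 row for deterioration during treatment, and 7.9.1 can be read as the more specific rule. One overlap is real: IgG given for an infection may also be a safety concern under Table 2, which asks for Visits 9 to 16 to be completed where possible. The texts need aligning.
- *Safety observation ends, or AE capture is cut on average.* AE capture falls short only for exits before Day 48, and over all exit days after dosing it is 2.5 days longer.
- *The rule hides IgG recovery.* Section 2.3 reports a 55% fall in serum IgG after one 10 mg/kg dose in healthy volunteers, so IgG replacement is conceivable. But IgG is a PD sample and not one of the scheduled clinical laboratory tests, so continuing those tests would not show its recovery.
- *Exits would fall unevenly between arms.* The documents give no evidence for this.

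**Conclusion.** The concern holds as a cheap improvement of low priority. Section 7.9.1 takes a patient out of the whole study for any listed medication, whatever the reason and even when no study drug remains, and scheduled laboratory tests and vital signs then stop after one ED visit. The cost per affected patient averages 3.4 of 8 laboratory visits and 1.9 of 6 vital-sign visits for exits after dosing, and reaches 7 and 5 for exit on Day 22. No average loss of AE capture is claimed. The averages assume equally likely exit days and an ED visit that fills exactly one later visit. That few patients are affected is a judgement, supported by the exclusion of planned vaccinations but not by any stated rate. No sample-size, power or alpha figure changes.

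**What to change.** **Protocol 7.9.1.** For a listed medication given for a reason other than MG rescue:
1. Stop any remaining study drug.
2. Do the Visit 16/ED set before the medication where possible; 7.9.2 already asks for this "prior to starting on rescue therapy wherever possible".
3. Continue scheduled safety assessments (laboratory tests, vital signs, ECG, AEs) through Visit 16, unless consent is withdrawn or the Investigator or Medical Monitor judges exit necessary. Keep AE follow-up for 30 days after the pre-medication set where that ends later, so that late cases lose nothing they have now.

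Add a matching row to Table 2, which also settles IgG given for an infection. Leave 7.9.2 unchanged. Total IgG and ADA sampling may continue at these visits for listing only.

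**SAP.**
- Map the pre-medication set as ED data are mapped now. Where that visit later has its own laboratory or vital-sign value, summarise the visit's value and list the other.
- Keep later safety values in the summaries, flagged as after a prohibited medication.
- List efficacy, PD and ADA values taken after the medication starts, and exclude them from all analyses, including the MMRM, the maximum-reduction ANCOVA and the tables and plots in SAP 18.
- State that such a medication does not by itself remove the patient's earlier values from the PD analysis set.

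**Cost.** A protocol amendment with written IRB/IEC approval (5.3.7), about four SAP sentences, and on average 4.4 (at most 8) already-scheduled visits per affected patient when the medication starts after dosing. The flag needs the medication's start date and indication. Section 7.9 requires all concomitant medications to be recorded but does not say that the indication is captured, so confirm this in the eCRF. Some later safety values may reflect the added medication.

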7.9.2 Rescue Therapy

Patients are eligible for rescue therapy as judged by the Investigator on the basis of parameters such as changes in MGQoL15r, MG-ADL, QMG, and MGC on any study day. Rescue therapy will be determined by the Investigator based on an overall clinical assessment and could include IVIg, PE, increase in the dose and frequency of SoC or any other treatment chosen by the Investigator. In this study, ARGX-113 may interfere with the efficacy or duration of efficacy of IVIg considering the half-life of IVIg. Additional details about ARGX-113 is present in [Section 2.2](#).

In case a patient needs rescue therapy according to the treating Investigator, the [Medical Director](#) at the Sponsor should be informed in addition to the [Medical Monitor](#) at the Sponsor's designated contract research organization (CRO, Quintiles); where possible prior to actual implementation of the rescue therapy.

If rescue therapy is administered, patients need to be discontinued from the study. For patients who discontinue the study early, all the procedures listed for the Early Discontinuation (ED) visit (same procedures as for the End-of-Study [EoS] visit or Visit 16) in the Schedule of Assessments ([Table 1](#)) are to be performed (early discontinuation visit) prior to starting on rescue therapy wherever possible.

7.10 Medical Care of Patients after End-of-Study

After a patient has completed the study or has withdrawn/discontinued early, usual treatment will be administered, if required, in accordance with the study site's SoC and generally accepted medical practice depending on the patient's individual needs. The Sponsor will not provide any additional care to patients after they withdraw/discontinue early or complete the study neither will the IMP be provided on a compassionate use program.

7.11 Treatment Compliance

The Investigator should promote compliance by stating that compliance is necessary for the patient's safety and the validity of the study. The prescribed dose, timing, and mode of

administration may not be changed. All dates and start and end time of IMP administration and any deviations from the intended regimen must be recorded.

7.12 Handling Missed Doses of the Investigational Medicinal Product

If the patient misses more than one dose of the IMP he/she may be replaced although may continue in the study and maybe evaluable for safety and efficacy evaluation, for details refer to [Table 2](#).

7.13 Accountability of Investigational Medicinal Product

The Investigator or delegated site staff is responsible for ensuring that the IMP received at the clinical site is inventoried and accounted for throughout the study.

Infusion of the IMP must be completed under the supervision of the Investigator, by a qualified member of the clinical staff. The Investigator or delegated site staff must maintain accurate records, demonstrating date and amount of IMP supplied and by whom.

The Sponsor's designated site monitor will periodically check the supplies of IMP held by the Investigator or pharmacist to ensure accountability and appropriate storage conditions of all IMP used.

Unused IMP must be accessible for verification by the site monitor during on-site monitoring visits. Used IMP should be kept on site and its accountability will be checked by the site monitor. Only after appropriate verification and confirmation from the site monitor, used IMP (vials) can be discarded/destroyed in accordance with the site procedures.

After the database lock, any remaining unused IMP will be returned to the Sponsor, or destroyed at the clinical site with the Sponsor's written permission (in this case a certificate of destruction will be provided and filed in the Trial Master File).

Hazardous materials such as used needles, syringes, and infusion bags, containing hazardous liquids, should be discarded immediately after use in a safe manner and must not be retained for drug accountability purposes or verification by the site monitor.

